9.4 TREATMENTS

9.4.1 Treatments Administered

The study drugs will be blinded and assigned to each subject based on the randomization schedule. The contents of each kit will be admixed immediately prior to administration by the investigator who will administer the drug to the patient at no colder than room temperature. The following treatments will be administered as a single dose via urethral catheter:

- URG101 treatment comprises the following:
 - 18 mL containing heparin sodium [REDACTED]
[REDACTED] Lidocaine HCl buffered to pH 7.4 (± 0.2) with 1X [REDACTED]
buffer, [REDACTED] [REDACTED]
[REDACTED]
[REDACTED]
- Placebo treatment comprises the following:
 - 18 mL 1X [REDACTED] buffer (pH 7.4 [± 0.2])
- Heparin treatment comprises the following:
 - 12 mL Heparin Sodium [REDACTED] plus 6 mL
3X [REDACTED] buffer (final mixture buffered to pH 7.4 [± 0.2])
- Lidocaine treatment comprises the following:
 - 12 mL Lidocaine HCl [REDACTED] plus 6 mL 3X [REDACTED] buffer
(final mixture buffered to pH 7.4 [± 0.2])

Prior to administering drug each subject will empty their bladder. Fifteen minutes later (± 5 minutes), the subject will complete the 11-point bladder pain NRS (requires a score of ≥ 5.0 to enter the trial and receive drug) and the 11-point urgency NRS (critical to administer 15 minutes (± 5 minutes) after voiding but no minimum score is required for study entry). These NRS scores will be the baseline scores for pain and

urgency. [REDACTED]

[REDACTED]

[REDACTED]

[REDACTED]

[REDACTED]

[REDACTED]

[REDACTED]

[REDACTED] The study medication is to be left indwelling for 45 minutes, with a minimum of 30 minutes, and after that may be voided by the subject. The test instruments will then be administered at the intervals listed in the schedule of assessments (Table 4).

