Study Design:	This is a Phase 2a, prospective, randomized, double-blind, placebo-controlled,

CLINICAL PROTOCOL SYNOPSIS (continued)

multicenter, single-dose, pharmacokinetic study designed to test the efficacy and safety of the combination product (URG101) versus its alkalized individual components (Heparin Sodium and Lidocaine Hydrochloride) and placebo [REDACTED]. A maximum of 300 subjects will be enrolled in Study URG101-105.

In this study, alkalized Lidocaine Hydrochloride Injection (20 mg/mL) and alkalized Heparin Sodium Injection (5,000 USPU/mL) will be subsequently referred to by the drug names Lidocaine and Heparin.

Eligible subjects exhibiting interstitial cystitis symptoms who have signed informed consent, will be screened and provisionally enrolled for intravesical treatment. Treatment may occur on the day of the Screening Visit (Visit 1) or any following day up to 1 week (Baseline and Drug Administration Visit 1a). If drug administration occurs on same day as screening then all assessments in Visit 1 and Visit 1a will be combined. If screening (V1), and baseline and drug administration (V1a) do not occur on same day, urine pregnancy test for women of childbearing potential and urine screen for drugs of abuse must be performed at both visits (V1 and V1a). Confirmation of symptom severity must be obtained before randomization: minimum pain score of 5 on the 11-point numerical rating scale [NRS] at Screening and 15 minutes (\pm 5 minutes) after voiding prior to study drug administration. Subjects will become fully enrolled upon receipt of acceptable qualifying laboratory evaluations (obtained via dipstick) and clinical assessments obtained before randomization.

At the Screening Visit (V1), the following will be completed: medical history and demographics; medication history; the Pelvic Pain and Urgency/Frequency (PUF) questionnaire; 11-point NRS for bladder pain and urgency; a physical examination, including a pelvic examination to confirm lower urinary tract tenderness; vital signs; blood and urine samples for safety laboratory assessments (including urine hematuria analysis); urine pregnancy test for women of childbearing potential; urine screen for drugs of abuse; and concomitant medications. (Note: results from a pelvic examination performed within 7 days prior to the Screening Visit (V1) may replace a V1 pelvic examination.)

[REDACTED]

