Subject Population:	Adult subjects, aged \geq 18 years, with Interstitial Cystitis who have moderate-to-severe symptoms of pain and/or urgency of bladder origin for at least 9 months, not currently taking narcotic pain medications, meeting the minimum screening scores.
Study Drug, Dose, Formulation, Method of Administration:	
URG101: buffered lidocaine and heparin, instillation via urethral catheter. URG101 treatment comprises the following:
 
 • 18 mL containing Heparin Sodium [REDACTED] 
Placebo treatment comprises the following:
 
 • 18 mL [REDACTED] 
Heparin treatment comprises the following:
 
 • 12 mL Heparin Sodium [REDACTED], plus 6 mL 3X [REDACTED] buffer [REDACTED] 
Alkalinized Lidocaine treatment comprises the following:
 
 • 12 mL Lidocaine HCl ([REDACTED]), plus 6 mL 3X [REDACTED] buffer [REDACTED]
Criteria for Evaluation:	
Primary Endpoint:
 
 1. A measure of the sum of bladder pain intensity differences from baseline to

CLINICAL PROTOCOL SYNOPSIS (continued)

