8.2 SECONDARY OBJECTIVES

The secondary objectives of the study are as follows:

1. To evaluate the change in bladder pain from baseline to 24 hours, using the sum of pain intensity differences (SPID-24) at defined time points, after administration of intravesical URG101 compared with alkalinized Lidocaine Hydrochloride Injection (20 mg/mL) alone, alkalinized Heparin Sodium Injection (5,000 USPU/mL) alone, and placebo [REDACTED]
2. To evaluate the change in urgency from baseline to 12 and 24 hours, using the sum of urgency intensity differences (SUID) at defined time points, after administration of URG101 compared with alkalinized Lidocaine Hydrochloride Injection (20 mg/mL) alone, alkalinized Heparin Sodium Injection (5,000 USPU/mL) alone, and placebo [REDACTED]
3. To evaluate the absolute and percentage change in bladder pain and urgency intensity differences at 1, 12, and 24 hours after administration of URG101 compared with alkalinized Lidocaine Hydrochloride Injection USP (20 mg/mL) alone, alkalinized Heparin Sodium Injection USP (5,000 USPU/mL) alone, and placebo [REDACTED]
4. To evaluate the change in improvement of symptoms using the Patient Global Assessment (question number 3) after treatment with URG101 compared with alkalinized Lidocaine Hydrochloride Injection (20 mg/mL) alone, alkalinized

Heparin Sodium Injection (5,000 USPU/mL) alone, and placebo (███████████) at 1, 12, and 24 hours

5. To evaluate the time to first administration of rescue medication for pain after treatment with URG101 compared to alkalinized Lidocaine Hydrochloride Injection (20 mg/mL) alone, alkalinized Heparin Sodium Injection (5,000 USPU/mL) alone, and placebo (███████████)
6. To investigate the relationship of plasma lidocaine concentrations at 1 hour after study drug administration to bladder pain and urgency at 1 hour, and from baseline to 12 and 24 hours, using the sum of pain and urgency intensity differences at defined time points, after treatment with URG101 compared with alkalinized Lidocaine Hydrochloride Injection USP (20 mg/mL) alone, alkalinized Heparin Sodium Injection USP (5,000 USPU/mL) alone, and placebo (███████████)
7. To evaluate the safety and tolerability of intravesical administration of URG101

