9.0 INVESTIGATIONAL PLAN

9.1 OVERALL STUDY DESIGN AND PLAN

This is a phase 2a, prospective, randomized, double-blind, placebo-controlled, multicenter, single-dose, pharmacokinetic study designed to determine the efficacy and safety of the combination product (URG101) versus its alkalinized individual components (Heparin Sodium and Lidocaine Hydrochloride) and placebo [REDACTED]
[REDACTED].

In this study, alkalinized Lidocaine Hydrochloride Injection (20 mg/mL) and alkalinized Heparin Sodium Injection (5,000 USP U/mL) will be subsequently referred to by the drug names alkalinized Lidocaine and alkalinized Heparin.

Eligible subjects exhibiting interstitial cystitis symptoms who have signed informed consent, will be screened and provisionally enrolled for intravesical treatment. Treatment may occur on the day of the Screening Visit (Visit 1) or any following day up to 1 week (Baseline and Drug Administration, Visit 1a). **If drug administration occurs on same day as screening then all assessments in Visit 1 and Visit 1a will be combined.** Confirmation of symptom severity must be obtained before randomization: minimum pain score of 5 on the 11-point numerical rating scale [NRS] at Screening and 15 minutes (\pm 5 minutes) after voiding prior to study drug administration. There is no minimum score requirement for the urgency NRS scales for patients to enter the study. Subjects will become fully enrolled upon receipt of acceptable qualifying laboratory evaluations and clinical assessments obtained before randomization.

On the day of study drug administration (V1a), subjects will be randomized (2:1:2:1; URG101:placebo:lidocaine:heparin) and will receive a single administration of one of four intravesical treatments in a blinded fashion, based on random assignment:

1. URG101 (buffered lidocaine-heparin)
2. Placebo: [REDACTED]
3. Lidocaine alone: [REDACTED]
4. Heparin alone: [REDACTED]

During the study, subjects will be allowed to take their protocol-allowed medications at their usual doses. Additionally, they may use only a short acting non-steroidal anti-inflammatory drugs (NSAIDs) as rescue medication, not sooner than 8 hours after receiving study medication and not within 6 hours prior to receiving study medication ([Table 1](#)).

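### Do the lidocaine and heparin arms hold 1.20 times the dose stated for URG101?

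*Combined protocol and SAP*

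**What the plan says.** Section 9.4.1 introduces the four treatments with "The following treatments will be administered as a single dose via urethral catheter". The lidocaine arm is "12 mL Lidocaine HCl [REDACTED] plus 6 mL 3X" buffer. The heparin arm begins "12 mL Heparin Sodium" and takes the same 6 mL of buffer. The synopsis repeats both lines: "12 mL Lidocaine HCl ([REDACTED]), plus 6 mL 3X" and "12 mL Heparin Sodium [REDACTED], plus 6 mL 3X". URG101 and placebo are each 18 mL in 1X buffer. The text after each component name, the amounts in URG101 and several lines just before the indwelling instruction are blacked out.

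The strengths are readable only in other places. Section 8.2 compares URG101 with "alkalinized Lidocaine Hydrochloride Injection (20 mg/mL) alone, alkalinized Heparin Sodium Injection (5,000 USPU/mL) alone, and placebo", and Section 9.1 defines the short names from "alkalinized Lidocaine Hydrochloride Injection (20 mg/mL) and alkalinized Heparin Sodium Injection (5,000 USP U/mL) will be subsequently referred to by the drug names". The synopsis and Section 9.7.1.2 print the same strengths.

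Section 7.5.1 gives 200 mg lidocaine with 50,000 units heparin as the dose proposed for this study. Section 7.4 also gives 200 mg as the lidocaine dose in URG101. No readable sentence states a total amount for either component arm. Section 9.4.2 refers to the Study Procedures Manual for preparation.

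**The concern.** Read together, the volume in one section and the strength in others give each component arm a fifth more drug than the rationale states. Nothing readable explains the difference.

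Section 9.2 says the study is there to learn whether heparin adds to the lidocaine effect and so justifies the combination. URG101 against lidocaine is one of the primary pairwise comparisons, and the synopsis sizes it separately (effect size 0.60, 60 subjects per group). If the lidocaine arm delivered 240 mg and URG101 200 mg, that comparison would mix heparin's contribution with a lidocaine dose difference. The analyses that relate plasma lidocaine to pain across arms would also need the true delivered amounts. If instead all arms were matched at the higher amount, the comparison would stand, but the dose rationale in Sections 7.4 and 7.5.1 would describe a different dose from the one given.

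**Working it through.** **Inputs**
- Drug volume in each component arm: 12 mL, plus 6 mL of 3X buffer, total 18 mL (synopsis; Section 9.4.1).
- Named strengths: 20 mg/mL lidocaine and 5,000 U/mL heparin (synopsis; Sections 8.2, 9.1 and 9.7.1.2).
- Stated dose: 200 mg and 50,000 U (Section 7.5.1; 200 mg also in Section 7.4).

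**Step 1. Can the stated dose be reproduced as volume × strength?**
- Strength applied to the 12 mL of drug: 12 × 20 = 240 mg and 12 × 5,000 = 60,000 U. Ratios: 240/200 = 1.20 and 60,000/50,000 = 1.20.
- Strength applied to the whole 18 mL mixture: 18 × 20 = 360 mg and 18 × 5,000 = 90,000 U, a ratio of 1.80 for both.

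Neither reading returns the stated dose. The first is the more natural, because Section 9.4.2 lists the two injections and the 3X buffer as separate supplies.

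**Step 2. Is 12 mL a plain misprint?** The buffer works out as 6 × 3/18 = 1X, which agrees with the 1X buffer in URG101 and placebo. The 12 + 6 split therefore looks deliberate.

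**Step 3. What would make the figures agree?**
- A smaller drug volume at the named strengths: 200/20 = 10 mL and 50,000/5,000 = 10 mL.
- A lower strength in 12 mL: 200/12 = 16.67 mg/mL and 50,000/12 = 4,167 U/mL.
- Partial instillation. The mixture holds 240/18 = 13.33 mg/mL or 60,000/18 = 3,333 U/mL, so the stated dose is in 200/13.33 = 15 mL and 50,000/3,333 = 15 mL.

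These are back-calculations to size the difference. None is printed in the readable text, and none is put forward as the right dose or volume.

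**Step 4. What would each reading mean for URG101 against lidocaine?**

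| Reading (assumption) | Lidocaine arm | URG101 | Ratio | Printed figures |
|---|---|---|---|---|
| One concentration in all arms, 15 of 18 mL instilled | 200 mg | 200 mg | 1.00 | all agree |
| One concentration in all arms, 18 mL instilled | 240 mg | 240 mg | 1.00 | rationale dose out of step |
| Hidden strength is 16.67 mg/mL, 18 mL instilled | 200 mg | 200 mg | 1.00 | product name out of step |
| URG101 holds 200 mg, lidocaine arm given in full | 240 mg | 200 mg | 1.20 | arms differ |

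What separates these rows is the strength in the treatment line, the URG101 content and the volume instilled. The public copy hides the first two, and no readable sentence gives the third.

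**The case for a change.** The strongest case for acting is that, in three of the four rows, either a printed figure is wrong or the arms differ. Only partial instillation clears everything, and the opening line of Section 9.4.1 reads naturally as giving the whole treatment. The check is cheap, and the trial's main question depends on the answer.

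Part of this stands. The multiplication is exact, the same 1.20 appears for both drugs, and nothing readable explains it. Asking whoever holds the full text is reasonable.

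The rest does not carry. Counting possible explanations says nothing about which is true, and the deciding facts sit in blacked-out text, which cannot be treated as absent from the plan. A reference to a single dose gives the number of administrations; it does not say that all 18 mL is instilled. The equal ratio for both drugs is also what one common instruction, such as an overfill with part instilled, would produce. Finally, 240 mg and 60,000 U are products derived here for the component arms, while 200 mg and 50,000 U are stated for URG101. No two readable sentences give different values for the same quantity.

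**Conclusion.** The concern does not lead to a change in the plan. From the public text, each component arm as prepared holds 1.20 times the stated URG101 amount (240 against 200 mg; 60,000 against 50,000 U), provided the named strengths apply to the 12 mL of drug. Whether the arms differ in what they deliver can be neither confirmed nor excluded: the ratio is 1.00 in three of the readings examined and 1.20 in one. No figure is shown to be wrong, and the amounts for each arm may already stand in the redacted text or the Study Procedures Manual.

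What remains is a clarification query of low to moderate confidence. The synopsis and Sections 7.4, 7.5.1, 8.2, 9.1, 9.4.1 and 9.7.1.2 have to be reconciled against the unredacted protocol and the manual, and a figure needs correcting only if they still disagree. No view is taken on which dose is right.

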9.4.2 Identity and Storage of Investigational Products

URG 101, Lidocaine HCl Injection, Heparin Sodium Injection, Placebo (1x [REDACTED] [REDACTED]) and diluent buffers (3X [REDACTED]) will be prepared by a Good Manufacturing Practice compliant contract manufacturing organization and shipped to the designated responsible person at each site for oversight and preparation of the medications for patient treatments as described in the Study Procedures Manual. A study drug preparation log and inventory accountability record of drug supplies will be kept at the clinical site or the pharmacy associated with the site.

9.4.3 Labeling of Investigational Products

All study drug will be labeled in accordance with text that is in full compliance with FDA regulations.

9.4.4 Storage Conditions

Drug kits will be stored at room temperature on-site in the clinic in an area accessible only to site staff.

Temperature monitoring is required at the storage location to ensure that the study drug is maintained within an established temperature range of 15 to 25C. The investigator or designee (or if regionally required, the head of the medical institution) is responsible for ensuring that the temperature is monitored throughout the total duration of the study and that records are maintained. The temperature should be monitored continuously by using either an in-house-validated data acquisition

system, a mechanical recording device (such as a calibrated chart recorder), or manual means, so that minimum and maximum thermometric values over a specific time period can be recorded and retrieved as required.

9.4.5 Method of Assigning Subjects to Treatment Groups

Subjects will be assigned to treatments based on a computer-generated, randomization scheme that will be reviewed and approved by an independent statistician. The randomization scheme and identification for each subject will be included in the final clinical study report for this study.

After the baseline period, subjects will be randomized to one of four treatment groups. Each treatment group will receive either URG101, placebo, lidocaine, or heparin as a single dose. The randomization ratio of the study is 2:1:2:1.

Randomization will be performed centrally by an interactive web response system (IWRS). The randomization schedule will be designed to randomly assign subjects to one of four treatment groups. The IWRS will generate the randomized identification numbers. At the time of randomization, the investigator or designee will use IWRS to register the subject information. The IWRS will assign each subject a unique 6-digit randomization number.

9.4.6 Prior and Concomitant Therapy

9.4.6.1 Prohibited Medications

Prohibited medications or therapies and restrictions for any drugs prior to receiving the double-blind study drug are provided in [Table 1](#).

Table 1. Prohibited Concomitant Medications and Restrictions

Medication or therapy	Restrictions and timing with respect to study drug administration
Local anesthetic via any route	Within 24 hours
Lidocaine patch	Within 14 days
Tricyclic antidepressants	Prohibited unless the subject has been on a stable dose of the medication for \geq 3 weeks
Gabapentin	Prohibited unless the subject has been on a stable dose \leq 1200 mg daily for \geq 3 weeks
Pregabalin	Prohibited unless the subject has been on a stable dose \leq 150 mg daily for \geq 3 weeks
Any pain medication other than short acting NSAIDs	Within 6 hours
Short acting NSAIDs	Within 6 hours but may be used as rescue medication 8 hours after study drug administration
Narcotics or medical marijuana	Within 3 weeks, except subjects on codeine may be admitted if use within this time period is not chronic and not within 6 hours of enrollment
Illegal drugs	Prohibited
Bladder instillation therapy	Within 7 days
Investigational device or drug	Within 30 days

9.4.7 Treatment Compliance

All study drug administration will be performed at the clinical site. Details of the study drug administration will be recorded on the CRF.

9.4.8 Drug Supplies and Accountability

In compliance with local regulatory requirements, drug supplies will not be sent to the investigator, or if regionally required, the head of the medical institution or the designated pharmacist, until the following documentation has been received by the sponsor:

- A signed and dated confidentiality agreement
- A copy of the final protocol signature page, signed and dated by both the sponsor and investigator
- Written proof of approval of the protocol, the ICFs, and any other information provided to the subjects by the institutional review board (IRB) or independent ethics committee (IEC) for the institution where the study is to be conducted

- A copy of the IRB- or IEC-approved ICF and any other documentation provided to the subjects to be used in this study
- The IRB or IEC membership list and statutes or Health and Human Services Assurance number
- A copy of the certification and a table of the normal laboratory ranges for the reference laboratory conducting the clinical laboratory tests required by this protocol
- An investigator-signed and dated Form FDA 1572, where applicable
- Financial Disclosure form(s) for the investigator and all subinvestigators listed on Form FDA 1572, where applicable
- A signed and dated curriculum vitae of the investigator including a copy of the investigator's current medical license or medical registration number on the curriculum vitae
- A signed and dated clinical trials agreement
- A copy of the regulatory authority approval for the country in which the study is being conducted (if required), and the import license (if required)

The investigator and the study staff, or if regionally required, the head of the medical institution or the designated pharmacist, will be responsible for the accountability of all study drugs and study supplies (dispensing, inventory, and record keeping) adherence to the sponsor's instructions and adherence to GCP guidelines as well as local or regional requirements.

Under no circumstances will the investigator allow the study drugs or study supplies to be used other than as directed by this protocol. Study drugs and study supplies will not be dispensed to any individual who is not enrolled in the study.

The site must maintain an accurate and timely record of the following: receipt of all study drugs and study supplies, dispensing of study drugs and study supplies to the subject, collection and reconciliation of unused study drugs and study supplies that are either returned by the subjects or shipped to the site but not dispensed to subjects, and return of reconciled study drugs and study supplies to the sponsor or (where applicable) destruction of reconciled study drugs and study supplies at the site. This includes, but may not be limited to: (a) documentation of receipt of study drugs and study supplies, (b) study drugs and study supplies dispensing and return reconciliation log(s), (c) study drugs and study supplies accountability log, (d) all shipping service receipts, (e) documentation of returns to the sponsor, and (f) certificates of destruction for any destruction of study drugs and study supplies that occurs at the site. All forms will be provided by the sponsor. Any comparable forms that the site wishes to use must be approved by the sponsor.

The study drugs and study supplies and inventory records must be made available, upon request, for inspection by a designated representative of the sponsor or a representative of a health authority (e.g., the FDA). Drug accountability will be reviewed during site visits and at the completion of the study.

